July 19, 2024

Protocol:

**Retrospective study on anti-cancer systematic therapy for
gastric cancer patients complicated with bleeding**

Retrospective study on anti-cancer systematic therapy for gastric cancer patients complicated with bleeding

Abstract

BACKGROUND

Hemorrhage isn't a rare complication with gastric cancer (GC)/gastroesophageal junction cancer (GEJC) and may lead to poor prognosis.

AIM

To investigate the impact of overt bleeding (OB) on the survival and treatment related adverse events (TRAEs) of GC/GEJC patients.

METHODS

This study will retrospectively enroll advanced or metastatic GC/GEJC patients who received systematic treatment at Peking University Third Hospital. The study aims to investigate the impact of OB on TRAEs for GC/GEJC patients receiving anti-cancer treatment, evaluate the risk factors of overt bleeding after treatment (OBAT), assess the influence of overt bleeding on the overall survival (OS).

Key words: Gastric cancer (GC)/gastroesophageal junction cancer (GEJC), Overt bleeding (OB), Systematic treatment

INTRODUCTION

Gastric cancer was the fifth most common cancer and ranked fourth for cancer mortality worldwide in 2020[1]. Hemorrhage wasn't a rare complication with gastric cancer (GC)/gastroesophageal junction cancer (GEJC). About 15.7% of GC/GEJC patients experienced bleeding[2]. Hemorrhage not only reduced the quality of life in GC/GEJC patients, but also led to poor prognosis even life-threatening if it was failure to timely stop and affected anti-cancer treatment[3, 4].

Risk factors for hemorrhage with GC/GEJC were various, including oldness, smoking history, chronic disease, use of antithrombotic/anticoagulants and so on[2, 5]. Radical gastrectomy was an ideal for early stage GC/GEJC with overt bleeding (OB),

but there was no curable chance for patients with advanced or metastatic GC/GEJC and hemostatic strategies such as endoscopic therapy, transcatheter arterial embolization were prone to rebleeding[4, 6, 7]. GC/GEJC patients with hemorrhage were less likely to receive chemotherapy due to poor physical quality and concern about treatment related adverse events (TRAEs) and rebleeding.

The retrospective study aims to investigate the impact of OB on TRAEs for GC/GEJC patients receiving anti-cancer treatment, assess the influence of overt bleeding on the overall survival (mOS).

PATIENTS AND METHODS

Data source and study patients

We will retrospectively enroll patients who were diagnosed with advanced or metastatic GC/GEJC at department of medical oncology and radiation sickness of Peking University third hospital. The eligibility criteria are as follows: 1) patients older than 18 years. 2) a histologically confirmed diagnosis of advanced or metastatic GC/GEJC. 3) the initial anti-cancer treatment was systematic therapy, including chemotherapy, targeted therapy or immune checkpoint inhibitor (ICI). 4) no history of gastrectomy before systematic therapy. The exclusion criteria included: 1) incompletable clinical data. 2) Siewert I type esophagus cancer.

The patients information collected from the database is as follows: age, gender, height, weight, Eastern Corporative Oncology Group Performance Status (ECOG-PS), chronic disease, drinking history, smoking history, diagnosis and metastatic sites, primary tumor location, histological grade, clinical stage according to the 8th edition of AJCC (American Joint Committee on Cancer) cancer staging manual, overt bleeding, symptoms, therapy strategy, tumor response to treatment, objective response rate (ORR), disease control rate (DCR), TRAEs and media overall survival (mOS).

Definitions

The diagnosis of OB is that the following conditions occurred one month before systematic treatment: 1) melena, hematemesis or hematochezia caused by gastric lesion, or 2) gastric hemorrhage confirmed by endoscopy. This study will only

analyze the impact of gastric overt bleeding (not including occult bleeding) on patients.

The radiographic best response to treatment will be assessed as complete response (CR), partial response (PR), stable disease (SD), no CR or no progressive disease (PD), or PD on the basis of response evaluation criteria in solid tumor 1.1 by clinicians. Objective response rate (ORR) is defined as the proportion of patients with the best response CR or PR. Disease control rate (DCR) is defined as the proportion of patients whose best response was CR, PR, no CR or no PD, or SD. Patients will be followed up at regular intervals. The criterion for terminating follow-up is death for any reason. OS is defined as the time from the first cycle of systematic therapy to death from any cause. TRAEs are evaluated according to the National Cancer Institute Common Toxicity Criteria version 4.0.

Statistical analysis

We will use SPSS version 25.0 (International Business Machines, New York, United States) to analyze the data and considered that differences are statistically significant if the two-sided P values are less than 0.05. The classified variables will be assessed by the χ^2 test or Fisher's exact test. A binary logistic regression model (entry method) will be used to identify items independently associated with OBAT. Odds ratios (ORs) and 95% confidence intervals (CIs) will be calculated. Survival curves will be estimated by the Kaplan-Meier method with the log-rank test. Hazard ratios (HRs) and 95%CIs will be calculated using the Cox proportional hazards model, and a check on the assumption of proportional risk will be conducted.

CONCLUSION

In conclusion, this study aims to evaluate the efficacy and safety of systematic therapy on GC/GEJC patients with bleeding. We hope the study will provide basis for future prospective clinical trial.

Institutional review board statement: This study was approved by the Peking University Third Hospital Medical Science Research Ethics Committee (IRB00006761-M2023544).

Informed consent statement: A waiver of informed consent was granted by the Ethics Committee.

REFERENCES

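### The Abstract and Methods define different cohorts and neither places the first cycle at this hospital, so any patient who started treatment elsewhere would bring immortal time into OS

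*Combined protocol and SAP*

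**What the plan says.** - **Population, Abstract (METHODS).** The study enrols "advanced or metastatic GC/GEJC patients who received systematic treatment at Peking University Third Hospital". The link to the hospital is treatment, with no restriction to the first cycle or first line.
- **Population, Data source and study patients.** The study enrols "patients who were diagnosed with advanced or metastatic GC/GEJC at department of medical oncology and radiation sickness of Peking University third hospital". The link is now diagnosis, and the place of treatment is not stated.
- **Eligibility criteria, same section.** Criterion 3 requires that "the initial anti-cancer treatment was systematic therapy" and criterion 4 requires "no history of gastrectomy before systematic therapy". Neither names a site. One exclusion is "incompletable clinical data", which is not defined.
- **Definitions.** "OS is defined as the time from the first cycle of systematic therapy to death from any cause". OB is bleeding in the month leading up to systemic treatment. Treatment-related adverse events (TRAEs) are given a grading scale but no start date or window.
- **Statistical analysis.** Survival is analysed by Kaplan-Meier, log-rank and Cox models in SPSS 25.0. Delayed entry and landmark analysis are not mentioned. Overt bleeding after treatment (OBAT) is analysed by logistic regression.

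**The concern.** Being treated at a hospital and being diagnosed at one of its departments select different patients, and each rule lets in a different problem.

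Under the Abstract rule, a patient who had several cycles elsewhere and then moved to this hospital qualifies. The OS clock starts at a cycle given before the patient could enter the database. Anyone who died in that interval never appears, so the interval is survival time guaranteed by selection. The month that decides OB status, and any early toxicity, also predate this hospital's care of the patient.

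Under the Methods rule, a patient diagnosed here before the first cycle and then treated elsewhere qualifies. That patient adds no immortal time, but toxicity and later bleeding may not reach this hospital's records.

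Between them, the two rules touch all of the stated aims: OS, TRAEs and the risk factors for OBAT.

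**Working it through.** The documents give no sample size, median OS, effect size or share of transferred patients, so there is no planned figure to reproduce. Everything below is an illustration on assumed inputs.

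**1. Effect on median OS**

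Assume exponential survival with true median m, so λ = ln 2 / m. A share f of the cohort enters d months after the first cycle, having survived to that point, and the clock still starts at the first cycle. For t > d the apparent survival is

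S(t) = (1 − f)·exp(−λt) + f·exp(−λ(t − d)).

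Setting S(t) = 0.5 gives

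apparent median = m + m·log2(1 − f + f·2^(d/m)).

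Example with m = 12, f = 0.2, d = 4: 2^(4/12) = 1.2599; 0.8 + 0.2 × 1.2599 = 1.0520; log2(1.0520) = 0.0731; 12 + 12 × 0.0731 = 12.88 months.

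Results for m = 12:

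| Transfer share f | Delay d (months) | Apparent median (months) | Shift |
|---|---|---|---|
| 10% | 1 | 12.10 | 0.10 |
| 10% | 4 | 12.44 | 0.44 |
| 20% | 4 | 12.88 | 0.88 |
| 30% | 4 | 13.30 | 1.30 |
| 40% | 4 | 13.71 | 1.71 |
| 20% | 6 | 13.38 | 1.38 |
| 40% | 6 | 14.65 | 2.65 |

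For f of 10-30% and d of 1-4 months, a true median of 8 months reads 8.10 to 9.35, and a true median of 16 months reads 16.10 to 17.27.

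Among patients who start elsewhere, the deaths that this cohort could never capture are 1 − 2^(−d/m). With m = 12 this is 5.6% at d = 1 and 20.6% at d = 4.

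**2. Effect on the OB hazard ratio**

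A Cox simulation used 20,000 patients per scenario, 30% with OB, median OS 12 months without OB, censoring at 36 months and d = 4. The naive fit starts everyone at the first cycle. The second fit uses the entry time.

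| True HR | Transfer share, no OB / OB | Naive HR | HR with entry time |
|---|---|---|---|
| 1.0 | 20% / 20% | 0.99 | 0.99 |
| 1.0 | 10% / 30% | 0.95 | 1.01 |
| 1.0 | 30% / 10% | 1.05 | 0.99 |
| 1.3 | 20% / 20% | 1.29 | 1.29 |
| 1.3 | 10% / 30% | 1.23 | 1.31 |
| 1.3 | 30% / 10% | 1.39 | 1.31 |

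Monte Carlo error: at HR 1.0 about 87.5% die by 36 months (1 − 2^(−3)), or about 17,500 events, so the standard error of log HR is about 1/√(17,500 × 0.3 × 0.7) ≈ 0.016. Differences of 0.01 to 0.02 are noise.

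A fourfold imbalance (10% versus 40%) with a 6-month delay is needed to move a true HR of 1.0 to about 1.11-1.12, or, with the shares reversed, to about 0.90-0.91.

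**3. Reading of the results**

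The median shifts whenever transfers are present. The OB comparison shifts materially only when the groups differ in transfer share or delay. Modelling the entry time returns the hazard ratio to its true value within simulation error.

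**The case against.** The strongest reply is that the two sentences should be read together: diagnosed at the department and treated at the hospital. A patient who transferred in mid-treatment would usually have been diagnosed elsewhere and so fails the Methods sentence. A patient diagnosed here and treated only elsewhere fails the Abstract sentence. This has force, and it makes the problem one of unclear wording. It is not a complete answer. The plan does not say that both conditions apply, and even together they do not place the first cycle here: someone diagnosed here, started elsewhere and treated here later passes both.

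A second reply is that the exclusion for deficient clinical data would remove transfers whose early history is unavailable. It might remove some. Because it is undefined, a patient with a referral summary could stay in, and removal would depend on the quality of the records.

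A third reply is that the main interest is the effect of OB, which is essentially unbiased when transfer patterns are similar in the two groups. That stands. The Introduction says that patients who bleed are less likely to receive chemotherapy, so different referral patterns are plausible. The direction is unknown, since such patients could die before transfer or be referred sooner.

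A reader might also infer three stronger points that the documents do not support:
- **That OS, OB and TRAEs all run from the first cycle.** Only OS is explicitly timed from it. OB is tied to the start of systemic treatment by implication, and TRAEs have no time anchor, which is a separate gap.
- **That unseen early events are coded as absent.** The plan does not say how they are recorded.
- **That transfers occurred.** The wording permits them but does not show them.

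**Conclusion.** The concern holds as a conditional one. The population statements disagree, the site of the first cycle is left open, OS starts at that cycle, and the planned survival methods make no allowance for late entry. If patients who started elsewhere are included, OS is overstated. The size of about 0.1 to 2.7 months rests on exponential survival, a true median of 12 months, and transfer shares and delays that are all assumed. It would be wrong to say that OS in this study is inflated, or that the OB hazard ratio is biased, as established facts. The hazard ratio moves only with unequal transfer share or delay, by about 5% in either direction for 10% versus 30% at 4 months. The immortal time comes mainly from the Abstract wording. The Methods wording, taken alone, carries the different risk of incomplete TRAE and OBAT capture. The disagreement between the two statements needs correcting even if the number of transfers proves to be zero.

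**What to change.** Put one population statement in both the Abstract and Data source and study patients, requiring that the first cycle of first systemic therapy was given at this hospital. Report how many patients the rule excludes.

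If transferred patients must be kept, record the date of first attendance here and use it as the entry time in the Kaplan-Meier and Cox analyses. Leave these patients out of the TRAE and OBAT analyses, and report their number by OB status. Delayed entry may need software other than the SPSS version named in the plan.

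Separately, state the period over which TRAEs are counted.

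The cost is one eligibility sentence that can be checked against the treatment record. The downside is a smaller cohort.

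### Exclusion 1 (incomplete clinical data) is not limited to pre-treatment fields, so its wording permits removing patients because an outcome is missing

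*Combined protocol and SAP*

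**What the plan says.** The exclusion is stated in Data source and study patients: "The exclusion criteria included: 1) incompletable clinical data". It gives no list of required fields, no time point, and no indication of who decides or whether they know the outcome.

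The next paragraph lists the data to be collected. After the baseline items it continues "overt bleeding, symptoms, therapy strategy, tumor response to treatment, objective response rate (ORR), disease control rate (DCR), TRAEs and media overall survival (mOS", so pre-treatment and post-treatment items stand in one list.

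Under Definitions, "The radiographic best response to treatment will be assessed as complete response (CR), partial response (PR), stable disease (SD", followed by a category between complete response and progression, and progressive disease. There is no category for a patient without a scan. "Objective response rate (ORR) is defined as the proportion of patients with the best response CR or PR"; DCR is built the same way. Neither says whether unscanned patients count in the denominator.

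For survival, "OS is defined as the time from the first cycle of systematic therapy to death from any cause", and "The criterion for terminating follow-up is death for any reason". No data cut-off and no last-date-alive rule is given. Statistical analysis names Kaplan-Meier, log-rank, Cox and logistic regression, but gives no missing-data method and defines no analysis population.

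The Abstract's aims include to "evaluate the risk factors of overt bleeding after treatment (OBAT), assess the influence of overt bleeding on the overall survival (OS"). Response rates are not among those aims; they bear only on the efficacy statement in the Conclusion.

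**The concern.** In a retrospective cohort the exclusion is applied to records that may already contain the outcome. If it covers any missing field, it can select patients on outcome in two ways. A patient who died before the first scan has no response value and no category to hold one. A patient lost to follow-up has no death date and no stated censoring date.

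OB is the exposure and OS the outcome of a stated aim. The Introduction itself describes bleeding as potentially life-threatening and as interfering with treatment, so early death that differs by OB group is plausible on the protocol's own premise. That is one of the settings in which dropping early deaths distorts the OB hazard ratio. Median OS, ORR and DCR could also shift, in directions that depend on who is dropped.

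**Working it through.** The documents give no sample size, event count, effect size or missing-data rate, so there is no planned figure to reproduce. The numbers below are illustrations, and every input is assumed: exponential OS with a 12-month median without OB; first scan at 2 months; three follow-up patterns, the same in both groups (everyone to 36 months; uniform 0-36; uniform 6-48). Hazard ratios come from a single-covariate Cox model on 1,000,000 simulated patients per group. Triplets follow the order of the three patterns.

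**1. Response rates.** Let s be the share unscanned and dropped.
- ORR, if none of them would have responded: 0.40/(1 - s). For s = 0.05, 0.10, 0.20 this is 42.1%, 44.4%, 50.0%.
- DCR, with d the share of the unscanned who lacked disease control: (0.75 - s(1 - d))/(1 - s). At s = 0.10, d = 1 gives 0.75/0.90 = 83.3%; d = 0.5 gives 0.70/0.90 = 77.8%; d = 0.25 gives 0.675/0.90 = 75.0%, no change. Being a non-responder is not enough, because stable disease counts as control.

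**2. Deaths before 2 months dropped in both groups.** With a constant hazard ratio of 1.5 the rule removes 1 - 2^(-2/12) = 10.9% without OB and 1 - 2^(-2/8) = 15.9% with OB. Medians rise from 12 to 2 + 12 = 14 months and from 8 to 2 + 8 = 10. With a threefold hazard in the first 2 months it removes 1 - 2^(-6/12) = 29.3% of the OB group. What remains is the hazard ratio after month 2:

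| OB effect | HR, all kept | HR, early deaths dropped |
|---|---|---|
| 1.5 throughout | 1.50 / 1.50 / 1.50 | 1.50 |
| 3 for 2 months, then 1.2 | 1.45 / 1.55 / 1.49 | 1.20 |
| 3 for 2 months, then 1.0 | 1.26 / 1.38 / 1.31 | 1.00 |

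**3. Early deaths dropped unequally, no true effect.** If all are dropped with OB and half without, 1.00 becomes 0.93 / 0.90 / 0.92. The reverse gives 1.07 / 1.11 / 1.09.

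**4. Lost patients dropped instead of censored.** Assume 20% lost per year in both groups: loss hazard l = -ln(0.8)/12 = 0.0186 per month, against a death hazard h = ln(2)/12 = 0.0578 without OB. With unlimited follow-up the retained patients have apparent hazard h + l, so a true 1.5 becomes (1.5h + l)/(h + l) = 0.1052/0.0764 = 1.38. With the assumed follow-up limits:
- A constant 1.50 becomes 1.42 / 1.46 / 1.44. Medians fall from 12 to 9.4 / 10.2 / 9.9 months and from 8 to 6.6 / 7.0 / 6.9. Censoring the same patients returns 1.50, 12 and 8.
- A true 1.00 stays 1.00 when loss is equal. If loss is 20% per year with OB and 10% without, dropping gives 1.12 / 1.08 / 1.10; the reverse gives 0.89 / 0.92 / 0.91. Censoring gives 1.00.
- For the effect confined to 2 months, dropping moves the ratio away from 1: about 1.27 to 1.31, 1.39 to 1.43 and 1.31 to 1.35 (a separate run, so starting values differ from the table by up to 0.01).

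**The case against.** The strongest reply is that a baseline-only rule was meant. The exclusion sits in the eligibility paragraph beside age, histology, first treatment, prior gastrectomy and Siewert type, all known before treatment. The data list says what will be extracted, not what must be complete, and ORR, DCR and median OS are cohort summaries that no single patient can lack. Also, "Patients will be followed up at regular intervals", and Kaplan-Meier and Cox accommodate living patients. This stands as far as intent goes. It does not close the gap, because no sentence confines the rule to baseline fields, and censoring helps only patients who are kept and have a defined censoring date.

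A second objection also stands in part. A patient who died before a scan has complete OS. Removal follows only if a missing response counts as incomplete clinical data, and items 2 and 3 of the working depend on that step.

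Three stronger readings are tempting but unsupported:
- That the plan will remove early deaths or lost patients. The documents show only that the wording permits it.
- That every patient still alive would be dropped, because follow-up ends only at death. That conflicts with the planned Kaplan-Meier and Cox analyses.
- That the OB hazard ratio must be biased. It is unchanged when all early deaths are dropped in both groups under a constant effect, and equal loss creates no effect where none exists.

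**Conclusion.** The concern holds as a defect of wording with a real consequence: as written, exclusion 1 can select patients on outcome, and nothing else in the document prevents it. It should be fixed. Confidence is medium, because the gap in the text is clear but its application is unknown.

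If unscanned patients are dropped, ORR is overstated when they would not have responded, and DCR is overstated to the extent that they lacked disease control. Median OS rises if early deaths are dropped and falls if lost patients are dropped. The OB hazard ratio for OS is biased if the dropping of early deaths differs by OB group or the OB effect is concentrated early. Dropping lost patients shrinks a constant effect modestly and can shift the ratio either way when loss is unequal. The magnitudes rest wholly on the assumed survival, scan time, follow-up and loss rates; neither size nor direction can be read from the documents.

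**What to change.** Limit exclusion 1 to missing data needed to establish eligibility (age, histology and stage, initial systemic therapy and first-cycle date, prior gastrectomy, Siewert type) and pre-treatment OB status. Keep every other patient who began a first cycle. That sentence cures the defect in the exclusion itself; three short additions settle how the retained patients are handled:
- Add a not-evaluable response category and keep those patients in the ORR and DCR denominators. Counting them as neither responding nor controlled is a common convention, but it is a choice and should be stated.
- Censor OS at the last date known alive, up to one common data cut-off.
- Report the number excluded by reason and by OB group.

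The cost is a few sentences of protocol text, one response category, a small table, and extraction of last-contact dates where not already held. ORR and DCR may look slightly less favourable, and there is a little more analysis work. Censoring lost patients is unbiased only if loss is unrelated to prognosis, so the change reduces the problem of loss to follow-up without removing it.

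### TRAEs have no common observation period and treatment duration is not collected, so crude TRAE proportions by bleeding status could understate, and with a large gap in course length hide or reverse, an excess risk

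*Combined protocol and SAP*

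**What the plan says.** The Abstract (METHODS) sets the aim: "The study aims to investigate the impact of OB on TRAEs for GC/GEJC patients receiving anti-cancer treatment". The Introduction repeats it, and the Conclusion gives the study a safety purpose.

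Under Definitions, TRAEs receive one sentence: "TRAEs are evaluated according to the National Cancer Institute Common Toxicity Criteria version 4.0". This fixes how severity is graded. It does not say when counting starts or stops. The only end of observation stated anywhere is general: "The criterion for terminating follow-up is death for any reason".

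Under Data source and study patients, the relevant part of the data list reads: "overt bleeding, symptoms, therapy strategy, tumor response to treatment, objective response rate (ORR), disease control rate (DCR), TRAEs". Number of cycles, last-dose date, treatment duration and TRAE onset date do not appear.

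Under Statistical analysis, "The classified variables will be assessed by the χ^2 test or Fisher's exact test", at a two-sided 0.05 level. Logistic regression has a different target: "A binary logistic regression model (entry method) will be used to identify items independently associated with OBAT". Kaplan-Meier, log-rank and Cox appear in the context of survival. No method is assigned to TRAEs by name.

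On why treatment might differ, the Introduction says that patients with hemorrhage were "less likely to receive chemotherapy due to poor physical quality and concern about treatment related adverse events (TRAEs) and rebleeding". It also says that bleeding can worsen prognosis and interfere with cancer treatment.

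**The concern.** The chance that a patient has had at least one TRAE rises with exposure to treatment. If the two groups are treated for different lengths of time, an ever/never comparison mixes the risk per unit of treatment with the amount of treatment given. Adjusting for baseline factors would not remove this, because course length arises after baseline. Two groups alike on every baseline item could still be compared over unequal exposure.

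As the plan stands, the imbalance could be neither adjusted for nor shown to a reader, because the fields that describe it are not on the data list. If OB courses are shorter, the error runs in the unsafe direction: too little apparent toxicity in bleeding patients, from a study meant to inform a later prospective trial.

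**Working it through.** **No figure to reproduce.** The documents give no TRAE rate, course length or sample size. Everything below is an illustration on assumed inputs.

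**Step 1: which analysis follows from the plan.** TRAE occurrence is a categorical variable. Logistic regression is assigned to bleeding after treatment, and the time-to-event methods sit with survival. The chi-square or Fisher test is what remains. This is an inference, but nothing in the plan contradicts it.

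**Step 2: effect of course length.** Assumed: 15% risk per cycle in OB, 10% in non-OB, and 8 cycles in non-OB. Three models, with the OB course varied from 8 to 3 cycles:

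- *A. Constant risk, everyone has exactly n cycles.* P = 1 − (1 − p)^n. Non-OB: 1 − 0.90^8 = 57.0%.
- *B. Constant risk, geometric course lengths with mean m.* With q = 1/m, P = 1 − q(1 − p)/[1 − (1 − q)(1 − p)]. Non-OB (m = 8): 1 − 0.1125/0.2125 = 47.1%.
- *C. Front-loaded hazard.* The 8-cycle hazard is −8 ln 0.90 = 0.843, with 60% in cycles 1–2 and the rest spread evenly over cycles 3–8. For n of at least 2, H(n) = 0.843 × [0.6 + 0.4(n − 2)/6]. OB rate ratio 1.5: P = 1 − exp(−1.5 H(n)). Non-OB: 57.0%.

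| OB cycles (n, or mean m in B) | A: OB vs 57.0% | B: OB vs 47.1% | C: OB vs 57.0% |
|---|---|---|---|
| 8 (equal exposure) | 72.8% | 58.5% | 71.8% |
| 7 | 67.9% | 55.3% | 69.3% |
| 6 | 62.3% | 51.4% | 66.6% |
| 5 | 55.6% | 46.9% | 63.6% |
| 4 | 47.8% | 41.4% | 60.4% |
| 3 | 38.6% | 34.6% | 57.0% |

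Under A, the true excess of 15.8 points at equal exposure falls to 10.9 at 7 cycles and 5.3 at 6. It is about level at 5 (−1.3) and reversed at 4 (−9.2). Break-even is n = 8 × ln 0.90 / ln 0.85 = 5.2 cycles. B gives the same pattern with smaller differences. Under C the excess is diluted throughout, vanishes only at 3 of 8 cycles and reverses only below that.

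**Step 3: no true effect.** With 10% per cycle in both groups under A, 4 OB cycles against 8 give 1 − 0.90^4 = 34.4% vs 57.0%, an apparent benefit of 22.6 points from course length alone. Under B the corresponding gap is 30.8% vs 47.1%, or 16.3 points.

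**Step 4: common window.** If all patients are observed over the first 2 cycles, A gives 1 − 0.85² = 27.8% in OB and 1 − 0.90² = 19.0% in non-OB. The direction is correct whatever happens later. The price is visible too: the non-OB proportion is 19.0% rather than 57.0%.

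**The case against.** The strongest reply is that the plan is silent rather than wrong. It names no TRAE analysis, and crude proportions are an inference from a general sentence on categorical variables. That is so. But following the plan as written leads there, and the missing exposure fields would leave no alternative at the analysis stage.

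A reader might infer that the protocol itself says OB patients have shorter courses. It does not. The remark about being less likely to receive chemotherapy concerns whether it is given, and eligibility already requires that initial treatment was systemic therapy. The sentence on prognosis and disturbed treatment is the only support; it is tied to failure to stop the bleeding in time and gives no duration. The influence of bleeding on survival is itself a study question.

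A reader might also infer that reversal is the expected outcome. The table does not support that: it needs a large gap in course length, and a larger one if toxicity comes early. Attenuation is the likelier result.

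Two further readings go too far. TRAEs are not confined to time on drug: nothing in the plan restricts recording in that way, and checkpoint inhibitors are among the eligible treatments. Nor are all treatment dates missing, since OS is counted from the first cycle and so needs that date.

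Finally, TRAEs over treatment as delivered are a legitimate descriptive quantity. They can be kept, provided they are not the only comparison and exposure is shown beside them.

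**Conclusion.** The point holds in conditional form. The plan leads to a crude comparison of TRAE proportions with no common observation period and no data on course length. If OB courses are shorter, any excess TRAE risk in OB patients is understated. On the assumed inputs the understatement runs from about 5 points at 7 vs 8 cycles (15.8 down to 10.9) to loss of the effect near 5 vs 8 and reversal at 4 vs 8; front-loaded toxicity makes it weaker. If courses are equal this bias is absent, and if OB courses are longer it runs the other way. The per-cycle risks, cycle numbers and shape of the hazard are assumptions. The size and direction of any real gap must come from the data, which the plan does not yet collect.

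**What to change.** In Definitions, state that the main comparison of TRAEs by OB status uses TRAEs with onset within a fixed calendar window from the first dose (for example 8 weeks). State also that whole-course TRAEs are reported as events per patient-month on treatment, including a fixed period after the last dose, beside the crude proportions. Calendar time is preferable to cycles because chemotherapy, targeted therapy and checkpoint inhibitors need not share a cycle length.

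Add number of cycles, last-dose date and TRAE onset date to the data list. The first-cycle date is already needed for OS.

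Report treatment duration by OB group, with deaths and stopping within the window, since a fixed window does not by itself equalise exposure when patients die or stop early. Tabulate reasons for stopping as well, because early stopping may be caused by toxicity.

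The cost is a few more chart fields and lower event counts in the main comparison, because the window drops late TRAEs, including late immune-related ones. The whole-course rates keep those in view.
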